### 1.3 Research hypothesis

Our hypothesis is that neoadjuvant therapy with anti-PD-L1 monoclonal antibody MEDI4736 in combination with anti-CTLA-4 monoclonal antibody tremelimumab will result in favorable alterations of the intratumoral immunologic environment in subjects undergoing resectional surgery for malignant pleural mesothelioma (MPM).

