Tumor tissues obtained either by thorascopic biopsy or by resectional surgery will be evaluated by time-of-flight mass spectrometry (CyTOF) to determine intratumoral CD8/Treg ratios and percentage of ICOS positive CD4 T cells, and by immunohistochemistry (Ventana assay) to determine the tissue expression of PD-L1. These variables will be compared before and after treatment (changes within the same patient tumor), or between treatment groups (MEDI-4736 alone, MEDI-4736+tremelimumab, untreated) following treatment. Additional hypothesis-generating analyses will include a comprehensive systems based evaluation of the intratumoral immune cell population composition and phenotype phenotype [e.g., dendritic cells, macrophages, myeloid derived suppressor cells (MDSC), neutrophils, T-cell subsets, natural killer (NK) cells, and B cells], and immune-related gene expression using the nanostring system within the tumors, blood, and bone marrow of patients in all treatment groups.

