## **TREATMENT PLAN**

### **5.3 Subject enrollment and randomization**

We expect to enroll a total of 20 evaluable subjects (if tissue obtained at time of thoracoscopy and time of surgical resection) with surgically resectable MPM to this study over a period of 24 months. Subjects will be randomized. Subjects will be assigned to one of the three treatments (n = 8 MEDI4736, n = 8 MEDI4736 + tremelimumab, and n=4 control). All subjects will undergo surgical resection one to six weeks after the infusion.

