### **10.1 Sample size**

**10.2** The primary objective is comparison of the ratio of CD8/Treg before and after treatment with combination MEDI4736+Tremelimumab. A total of 20 evaluable subjects (if tissue obtained) will be enrolled in this study for 24 months and 8 subjects will be assigned to combination MEDI4736+Tremelimumab (8 subjects to MEDI4736 only and 4 subjects to control). The outcome of interest in this study is a change in ratio of CD8/Treg before and after treatment with combination MEDI4736+Tremelimumab within subjects. There are no data available to estimate a change of ratio of CD8/Treg before and after the treatment but in our pilot data from 6 subjects with MPM the log transformed ratio of CD8/Treg was approximately normally distributed with a mean of 1.94(6.96 in raw scale) and standard deviation of 0.808(2.24 in raw scale). Assuming that repeat values are moderately correlated( $r=0.5$ ), then the difference between before and after the combination treatment will also have a standard deviation of 0.808(2.24 in raw scale). We estimate that we will have 80% power ( $\alpha=5\%$ , a paired t-test) to detect an increased log ratio CD8/Treg of 2.87(17.71 in raw scale) after the combination treatment with 8 subjects.

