### **10.3 Analysis plan**

There will be two treatment arms (MEDI4736 only and combination MEDI4736+tremelimumab) and one untreated arm (control). Randomization, stratified by receiving previous chemotherapy or not, will help to minimize patient selection biases between three arms. Preliminary tests will be performed to assess whether our data is normally or non-normally distributed. Patient characteristics will be summarized descriptively. Baseline characteristics will be compared by treatment assignment. For our primary objective that compares outcome variable in tissues before and after treatment with combination MEDI4736

Clinical Study Protocol

Drug Substance Tremelimumab

Study Number **ESR-14-10744**

Edition Number 8

Date 17 April 2019

and tremelimumab, we will use a paired t-test in log-transformed ratio of intratumoral cytotoxic T cells to regulatory T cells (CD8/Treg) before and after the treatment. In our secondary objective numerous variable comparisons are made between tumor tissues from untreated patients with from patients undergoing treatment with either MEDI4736 or MEDI4736 + tremelimumab, and between tumor tissues from patients undergoing treatment with MEDI4736 and tumor tissues from patients undergoing treatment with MEDI4736+tremelimumab. In these comparisons, a paired t-test or Student t-tests will be performed. Because approximately 20 comparisons of immune cell populations will be performed, a Bonferroni correction will be applied to correct for multiple comparisons. For the comparison of overall survival and recurrence-free survival between treatment groups, log-rank test will be used. These analysis will be post-protocol analysis based upon data obtained from the standard of care follow up in our post-surgical patients. SAS software will be used for all other statistical analyses.

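### The primary before/after test has no control, and the plan's one controlled comparison on the same marker ignores baselines that are collected anyway

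*Combined protocol and SAP*

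**What the plan says.** The hypothesis in section 1.3 is causal: the combination "will result in favorable alterations of the intratumoral immunologic environment in subjects undergoing resectional surgery". The primary objective (2.1), the sample size (section 10, sample size text) and the primary test all concern the change within the combination arm. Section 10.3 states the test as "we will use a paired t-test in log-transformed ratio of intratumoral cytotoxic T cells to regulatory T cells (CD8/Treg) before and after the treatment".

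The trial also randomises an untreated arm, 2:2:1 after the biopsy (5.3.1), which gives 8, 8 and 4 patients. Section 5.3 counts all 20 as evaluable "if tissue obtained at time of thoracoscopy and time of surgical resection", so controls supply the same two samples as treated patients.

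Controls enter the analysis of this marker through secondary objective 3 (2.2), which compares CD8/Treg in combination patients with MEDI4736 alone and, separately, with untreated patients. Section 3.1 reserves change for comparisons within the same patient's tumour and describes the other comparisons as "between treatment groups (MEDI-4736 alone, MEDI-4736+tremelimumab, untreated) following treatment". Section 10.3 gives these secondary comparisons a paired or Student t-test and a Bonferroni correction for about 20 comparisons of immune cell populations. Nowhere does the plan compare change in the combination arm with change in the control arm, or adjust a between-arm comparison for baseline.

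**The concern.** Before and after differ by more than the drug. The first sample is a small thoracoscopic biopsy and the second comes from a whole resection. The second is also taken from a tumour that was surgically biopsied 10 to 63 days earlier in treated patients (3 days + 1 week, up to 3 weeks + 6 weeks). If specimen type or the earlier procedure moves CD8/Treg, the paired test responds to that just as it responds to drug.

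What is at stake is the conclusion that a significant primary result can carry. The hypothesis attributes the change to treatment, while the primary test shows only that a change occurred. The material for a better controlled estimate is already being collected, but the plan leaves the baselines out of it.

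**Working it through.** **Inputs.** From the sample size text: log-scale mean 1.94 and SD 0.808 (six pilot subjects), an assumed correlation r = 0.5, a target log ratio of 2.87, n = 8, alpha 5%. Planned effect: 2.87 - 1.94 = 0.93 log units, and exp(0.93) = 2.53-fold. Allocation 8 v 4 is from 5.3. Sidedness is not stated.

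**1. The plan's own figure.** SD of change = 0.808 × √(2 × (1 - 0.5)) = 0.808, which agrees with "the difference between before and after the combination treatment will also have a standard deviation of 0.808(2.24 in raw scale". Noncentrality = (0.93/0.808) × √8 = 3.26 with 7 df. Two-sided power is 79.7%, so the stated 80% reproduces. One-sided power would be 89.9%, so two-sided is the intended reading.

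**2. Primary test with no drug effect.** Same test, two-sided 5%, noncentrality = ln(shift)/0.808 × √8. The shifts are assumptions.

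| Upward shift from biopsy to resection | Chance of a significant result |
|---|---|
| none | 5.0% |
| 1.2-fold | 8.6% |
| 1.5-fold | 23% |
| 2.0-fold | 55% |
| 2.53-fold (the planned effect) | 80% |

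In the other direction, a true 0.93 effect combined with a 1.5-fold downward shift leaves a net 0.93 - 0.405 = 0.525, and power falls from 80% to 35%.

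**3. Objective 3 as planned (post-treatment values, 8 v 4).** SE = 0.808 × √(1/8 + 1/4) = 0.495. With 10 df, t = 2.228, so the half-width is 1.10 log units and the 95% CI is about ×/÷ 3.0. Power at 0.93 is 40% at the 5% level. If Bonferroni over 20 applies (0.05/20 = 0.0025), it is about 6%.

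**4. Change-score contrast, combination minus control.** At r = 0.5 the SD of change is again 0.808, so SE and power equal those in step 3. At r = 0.3 it is worse (SD 0.956, power 30%); at r = 0.7 it is better (SD 0.626, power 59%).

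**5. ANCOVA on log baseline (two arms, 9 df).** Residual SD = 0.808 × √(1 - r²). At r = 0.5 this is 0.700, so SE = 0.700 × √(3/8) = 0.429. The half-width is 2.262 × 0.429 = 0.97, giving a 95% CI of about ×/÷ 2.6 and power of 49%.

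These figures take the two arms to have equal mean baselines. With only 12 patients, chance imbalance inflates the variance by 1 + 1/(12 - 4) = 1.125 on average. The SE then becomes 0.429 × √1.125 = 0.455 and power about 45%.

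| r | Post-treatment values | Change score | ANCOVA, equal baselines | ANCOVA, average imbalance |
|---|---|---|---|---|
| 0.3 | 40% | 30% | 42% | 38-39% |
| 0.5 | 40% | 40% | 49% | 45% |
| 0.7 | 40% | 59% | 65% | 60% |

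**6. Control arm's own change (n = 4).** Half-width = 3.182 × 0.808/√4 = 1.29, a 95% CI of about ×/÷ 3.6. It is descriptive only.

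**The case against.** The strongest reply is that a randomised comparison on this marker is already planned. Randomisation follows the biopsy, so a shift common to all arms cancels in expectation when resection values are compared under objective 3. That stands. A reader might infer that the control arm goes unused, or that the trial as a whole would mistake a sampling shift for a drug effect. The documents do not support either reading; the weakness belongs to the primary test read alone. Nor is the type I error of the paired test wrong for the objective in 2.1, which is a before/after comparison. The problem is attribution to treatment under 1.3.

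Second, simply subtracting the control change would gain nothing at the plan's r = 0.5 and would lose precision below it. That also stands, and it is why the remedy is baseline adjustment.

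Third, footnote i to the Schedule of Study Assessments lets controls go directly from thoracoscopy to resection. Their interval may be shorter than 10 to 63 days, so their change need not carry the same time or wound effects. It does still reflect the difference between biopsy and resection specimens. This limits any controlled estimate, including objective 3 as planned.

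Fourth, the shift sizes are assumed. The percentages in step 2 are points on the test's power curve and are no evidence that a shift exists. Fifth, section 10 calls this a pilot. That bears on severity, but a pilot with a causal hypothesis and a randomised control still needs a conclusion that its analysis supports.

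Objective 3's reference to a ratio of the CD8/Treg ratio could be read as a fold change. Section 3.1 points to post-treatment values instead, so at best the text is ambiguous.

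**Conclusion.** The point holds in a limited form. The primary paired test is uncontrolled, so a significant result establishes a change from biopsy to resection and not, by itself, a treatment effect. The size and direction of any background shift are unknown. Over an assumed 1.2- to 2.0-fold upward range, the test would be significant in 8.6% to 55% of trials with no drug effect.

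The existing safeguard, objective 3, is valid in principle against a common shift. It is weak in practice: 40% power, or about 6% under Bonferroni, with no use of baseline.

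Baseline adjustment improves on it modestly under the plan's SD of 0.808 and r = 0.5: 45-49% power. If r is nearer 0.3 there is practically no gain; at 0.7 the gain is large. No analysis of four controls makes this a powered comparison. Severity: should-fix, because the primary test and data collection are sound for the stated before/after objective and the remedy is an added estimate and clearer reporting.

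**What to change.** In section 10.3:

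1. Keep the paired t-test in the combination arm as the primary test.
2. Specify objective 3 for CD8/Treg, combination against control, as an ANCOVA of log resection ratio on arm and log baseline ratio. Report the combination-minus-control difference with its 95% CI as the key supportive estimate, outside the Bonferroni set.
3. Beside the primary result, report the control arm's paired log change with 95% CI and each arm's biopsy-to-resection interval, noting that control intervals may be shorter.
4. Describe the primary result as change from biopsy to resection, and rest any attribution to treatment on the controlled estimate.

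The cost is wording only: no new patients, samples or assays, and no change to the primary test or its power. Prespecification matters because the study is open-label, and showing or omitting four controls' results after the fact would be open to selection. The downside is a wide interval (about ×/÷ 2.6 at best at r = 0.5) and a more modest claim.

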### **2.2 Secondary objective(s)**

The secondary objectives of this study are:

- 1) Comparison of the percentage of inducible T-cell co-stimulator (ICOS) positive intratumoral CD4 T cells before and after treatment with combination MEDI-4736 and Tremelimumab checkpoint inhibitor therapy.
- 2) Comparison of tumor tissue expression (Ventana assay) of programmed death-ligand 1 (PD-L1) before and after treatment with combination MEDI-4736 and Tremelimumab checkpoint inhibitor therapy.
- 3) Comparison of the ratio of the intratumoral CD8/Treg ratio in patients treated with combination therapy (MEDI-4736 and Tremelimumab) compared to either patients treated with MEDI-4736 alone, and separately compare to untreated patients.
- 4) Comparison of the percentage of inducible T-cell co-stimulator (ICOS) positive intratumoral CD4 T cells in patients treated with combination therapy (MEDI-4736 and Tremelimumab) compared to either patients treated with MEDI-4736 alone, and separately compare to untreated patients.

- 5) Comparison of tumor tissue expression (Ventana assay) of programmed death-ligand 1 (PD-L1) in patients treated with combination therapy (MEDI-4736 and Tremelimumab) compared to either patients treated with MEDI-4736 alone, and separately compare to untreated patients. These analysis will be post-protocol analysis based upon data obtained from the standard of care follow up in our post-surgical patients.
- 6) Comparison of overall survival in patients treated with either MEDI-4736 alone or MEDI-4736 plus Tremelimumab with historical untreated controls. These analysis will be post-protocol analysis based upon data obtained from the standard of care follow up in our post-surgical patients.
- 7) Comparison of recurrence-free survival in patients treated with either MEDI-4736 alone or MEDI-4736 plus Tremelimumab with historical untreated controls. These analysis will be post-protocol analysis based upon data obtained from the standard of care follow up in our post-surgical patients.

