#### **5.3.1 Procedures for randomization**

After mediastinoscopy + thoracoscopy, eligible subjects with MPM will be randomized in 2:2:1 ratio to one of three arms: MEDI4736 alone, MEDI4736 + tremelimumab, and a control group of neither MEDI4736 nor tremelimumab. A computer-generated randomization scheme may be generated by the Biostatistics Core, Baylor College of Medicine. Randomization will be accomplished via access to a secure website developed by the Biostatistics Core and automatically notified to the study coordinator or the investigator via email. Randomization will be stratified by receiving previous chemotherapy or not.

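### Between-arm CD8/Treg (secondary objective 3): no baseline-adjusted analysis is specified, although a pre-randomisation value is planned for every evaluable patient; a cheap gain in precision if the plan's r=0.5 is near the truth

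*Combined protocol and SAP*

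**What the plan says.** Objective 3 in Section 2.2 compares intratumoral CD8/Treg in the combination arm with MEDI4736 alone and, separately, with untreated patients. Section 3.1 says the variables are compared within patient, "or between treatment groups (MEDI-4736 alone, MEDI-4736+tremelimumab, untreated) following treatment". For the secondary comparisons Section 10.3, like the synopsis, names only this: "In these comparisons, a paired t-test or Student t-tests will be performed". It also says "Baseline characteristics will be compared by treatment assignment", but no between-arm analysis takes the baseline ratio or the chemotherapy stratum as a covariate.

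A baseline value is planned in every arm:

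- Section 5.3 counts "20 evaluable subjects (if tissue obtained at time of thoracoscopy and time of surgical resection" and splits them 8 / 8 / 4.
- Section 5.3.1 places randomisation after the biopsy: "After mediastinoscopy + thoracoscopy, eligible subjects with MPM will be randomized in 2:2:1 ratio to one of three arms".
- Section 3.1 has CD8/Treg measured by CyTOF on both the biopsy and the resection tissue, and the synopsis gives CyTOF first call on tissue.

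Section 10.1 assumes a correlation of 0.5 between repeat log ratios, while stating "There are no data available to estimate a change of ratio of CD8/Treg before and after the treatment". From that correlation it derives that "the difference between before and after the combination treatment will also have a standard deviation of 0.808".

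**The concern.** A covariate measured before randomisation, on the same scale as the outcome, is usually the most useful one available. With arms of 8, 8 and 4, a difference in baseline ratio can arise by chance. At r=0.5 a post-treatment-only comparison carries about half of that difference into the estimated arm effect. The combination-versus-control contrast is also the only randomised comparison that can be set beside the primary before/after test, which has no control, and it rests on 8 v 4 patients. At stake is the precision of that contrast and of combination versus monotherapy. There is also a choice between post-treatment values and change scores that the text leaves open until the data are seen.

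**Working it through.** **Inputs.** From Section 10.1: SD of the log ratio 0.808, r=0.5, log means 1.94 and 2.87. From Section 5.3: arms 8 / 8 / 4. The plan names no confidence intervals for these comparisons; interval width is used here as a measure of precision.

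**The plan's own figure.** Paired t-test, n=8, difference 2.87 - 1.94 = 0.93, SD of change 0.808 × √(2(1 - 0.5)) = 0.808. The non-centrality is 0.93/0.808 × √8 = 3.26, and two-sided power is 79.7% (80.0% using ln(17.71/6.96) = 0.934). The stated 80% reproduces.

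**Unadjusted 95% half-width**, t(N-2) × 0.808 × √(1/n1 + 1/n2):

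- 8 v 8: 2.145 × 0.808 × 0.500 = 0.866
- 8 v 4: 2.228 × 0.808 × 0.612 = 1.102

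**Adjusted for baseline, same two arms.** Multiply by √(1 - r²), use t(N-3), and allow for chance baseline imbalance with √(1 + 1/(N-4)):

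- 8 v 8: 2.160 × 0.404 × 0.866 × 1.041 = 0.787; ratio 0.866/0.787 = 1.10
- 8 v 4: 2.262 × 0.495 × 0.866 × 1.061 = 1.028; ratio 1.102/1.028 = 1.07

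Simulation (100,000 trials per design) agrees. The unadjusted interval is wider by 10.8% in median and 10.4% in mean width for 8 v 8, and by 8.7% and 7.9% for 8 v 4. In single trials at r=0.5 the adjusted interval is the narrower one in about 72% (8 v 8) and 61% (8 v 4).

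**Change scores.** Their SD is 0.808 × √(2(1 - r)), which is again 0.808 at r=0.5. Post-only carries +0.5 of a baseline difference into the estimate and a change score carries -0.5, so neither has the advantage.

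**Dependence on r** (median width of each t-test relative to the two-arm adjusted analysis, by simulation):

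| r | post-only, 8 v 8 | post-only, 8 v 4 | change score, 8 v 8 | change score, 8 v 4 |
|---|---|---|---|---|
| 0 | 0.96 | 0.94 | 1.36 | 1.33 |
| 0.3 | 1.01 | 0.99 | 1.19 | 1.17 |
| 0.5 | 1.11 | 1.09 | 1.11 | 1.09 |
| 0.7 | 1.35 | 1.32 | 1.04 | 1.02 |

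Against post-only, break-even is at r of about 0.28 to 0.30 (8 v 8) and 0.34 to 0.36 (8 v 4), by median or mean width.

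**Three-arm model at r=0.5.** Median half-widths with baseline are 0.747 (8 v 8) and 0.915 (8 v 4), against about 0.846 and 1.065 for the t-tests: the t-test intervals are 13% and 16% wider. Pooling the variance over three arms accounts for 1% and 4% without any use of baseline (half-widths 0.835 and 1.023). Adding the stratum gives 0.752 and 0.921.

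**Power.** I assume a combination effect of 0.93 log against control, borrowed from the within-arm target, with r=0.5 and two-sided 5%. Power is 40% for the t-test, 45% with baseline in two arms, and 50% for the three-arm model with baseline and stratum. If the Bonferroni correction over about 20 comparisons covers objective 3, which Section 10.3 does not say, the t-test has 6% and that model 11%.

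**Chance imbalance.** The SE of a baseline difference is 0.808 × √(1/n1 + 1/n2) = 0.404 (8 v 8) or 0.495 (8 v 4). The chance that it exceeds 0.5 log in either direction is 22% or 31%.

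**The case against.** The strongest reply is that this is a preference for efficiency, not an error. Baseline precedes randomisation, so the planned t-tests are valid and unbiased over randomisation. Section 10 calls the study a pilot, no stated decision rests on these contrasts, and power stays low either way. The benefit rests on a correlation the plan assumes without data. All of this stands, and it sets the weight of the point.

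Four stronger readings are tempting, and the documents do not support them:

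- *The plan ignores baseline altogether.* Section 10 describes the endpoint as a before-and-after ratio, so t-tests on change scores are not excluded, although Section 3.1 points to post-treatment values. At r=0.5 change scores do no better than post-only; at r=0.7 they recover most of what adjustment gives.
- *A paired test is misapplied to different patients.* The sentence in Section 10.3 covers the secondary comparisons generally, and objectives 1 and 2 are before/after comparisons for which pairing is right.
- *Serious baseline imbalance is to be expected.* The chances above are 22% and 31%, at a threshold chosen for illustration. That is possible, not probable.
- *The gain against monotherapy can be sized from the mouse data in the synopsis.* Those figures are for two single agents; no combination value is given there.

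Adjustment also leaves untouched the unequal time from biopsy to resection, since footnote i of the schedule lets controls go straight to surgery.

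**Conclusion.** The point holds as a cheap improvement to a secondary analysis. The plan specifies no baseline-adjusted between-arm analysis of CD8/Treg, while planning the pre-randomisation measurement that would support one. Under the plan's own SD and r=0.5, either t-test costs about 11% of typical interval width for 8 v 8 and 7-9% for 8 v 4, the range reflecting how widths are averaged. With baseline alone, adjustment makes the interval about 4-6% wider than post-only at r=0. At r=0.7 the post-only interval is about 30% or more wider than the adjusted one. These are averages over trials and assume a usable CyTOF value at both times, a common slope and a common variance. A reader might infer biased arm differences or a weakened primary result. Neither follows: randomisation protects the first, and the primary paired t-test within the combination arm does not use these comparisons.

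**What to change.** In Section 10.3 and the synopsis, replace the between-arm CD8/Treg t-tests with one linear model over all 20 evaluable patients: log post-treatment ratio on arm and log baseline ratio, with the prior-chemotherapy stratum as a design term for which no precision gain is claimed. Report combination/monotherapy and combination/control fold differences with 95% confidence intervals. Give the two-arm baseline-adjusted result as a sensitivity check, and leave the primary paired t-test as it is.

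The cost is wording only: no new patients or samples. The text should name the downside:

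- **Degrees of freedom.** One or two are spent, leaving 20 - 3 - 1 - 1 = 15 with the stratum. The stratum costs about 0.6% of width if balanced across arms, and 0.6-1.6% under stratified blocks of 5 or 10; Section 5.3.1 gives no block size.
- **Common slope and variance.** With slopes of 0.2 / 0.5 / 0.8 (combination / monotherapy / control), simulated type I error for 8 v 8 is 5.9%, against 5.0% for the t-test.
- **Low correlation.** At r=0 the model with baseline and stratum gives an interval about 3% wider than the t-test for 8 v 8, and about the same for 8 v 4.

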### **Statistical Methods and Data Analysis:**

There will be two treatment arms (MEDI4736 only and combination MEDI4736+tremelimumab) and one untreated arm (control). Randomization, stratified by receiving previous chemotherapy or not, will help to minimize patient selection biases between three arms. Preliminary tests will be performed to assess whether our data is normally or non-normally distributed. Patient characteristics will be summarized descriptively. Baseline characteristics will be compared by treatment assignment. For our primary objective that compares outcome variable in tissues before and after treatment with combination MEDI4736 and tremelimumab, we will use a paired t-test in log-transformed ratio of intratumoral cytotoxic T cells to regulatory T cells (CD8/Treg) before and after the treatment. In our secondary objective numerous variable comparisons are made between tumor tissues from untreated patients with from patients undergoing treatment with either MEDI4736 or MEDI4736 + tremelimumab, and between tumor tissues from patients undergoing treatment with MEDI4736 and tumor tissues from patients undergoing treatment with MEDI4736+tremelimumab. In these comparisons, a paired t-test or Student t-tests will be performed. Because approximately 20 comparisons of immune cell populations will be performed, a Bonferroni correction will be applied to correct for multiple comparisons. For the comparison of overall survival and recurrence-free survival between treatment groups, log-rank test will be used. These analysis will be post-protocol analysis based upon data obtained from the standard of care follow up in our post-surgical patients. SAS software will be used for all other statistical analyses.

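### Holm's step-down procedure would be a free but small improvement on single-step Bonferroni for the roughly 20 immune-cell comparisons

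*Combined protocol and SAP*

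**What the plan says.** The analysis plan in Section 10.3 treats the primary CD8/Treg comparison on its own, as one paired t-test on the log scale within the combination arm. Section 10.1 powers that test at 5%.

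The plan then turns to the secondary comparisons between untreated, monotherapy and combination tissue: "In these comparisons, a paired t-test or Student t-tests will be performed". The next sentence sets the multiplicity rule: "Because approximately 20 comparisons of immune cell populations will be performed, a Bonferroni correction will be applied to correct for multiple comparisons". The synopsis repeats it under Statistical Methods and Data Analysis: "a Bonferroni correction will be applied to correct for multiple comparisons".

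Neither place states a family-wise level, lists the comparisons, plans simultaneous confidence intervals, or says why a single-step method was chosen. Section 3.1 describes the broad immune-cell evaluation as hypothesis-generating, and Section 10 calls the trial a pilot.

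**The concern.** With 20 comparisons and a family-wise 5%, Bonferroni holds every comparison to 0.05/20 = 0.0025, however many of the others have already been rejected. Holm starts at the same 0.0025 and relaxes the threshold after each rejection, with the same error guarantee. A trial with 8, 8 and 4 subjects has little power to spare. The stake is that some real immune-cell changes would be called non-significant when the chosen error rate would have allowed them to be declared.

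**Working it through.** **Inputs from Section 10.1.** Log CD8/Treg has baseline mean 1.94 and SD 0.808, and repeat values are correlated at 0.5. The design is meant "to detect an increased log ratio CD8/Treg of 2.87(17.71 in raw scale) after the combination treatment with 8 subjects". Arms are 8, 8 and 4.

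**Assumptions, because the plan is silent.** The family has exactly 20 tests, family-wise alpha is 5% two-sided, and the CD8/Treg SD and effect apply to every marker. SD 0.808 is also used for the between-arm tests.

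**Step 1: reproduce the plan's figure.**
- SD of the difference = √(2 × 0.808² × (1 − 0.5)) = 0.808.
- Effect = 2.87 − 1.94 = 0.93, and 0.93/0.808 = 1.15 SD.
- Noncentral-t power for a paired test with 7 degrees of freedom at two-sided 5% is 79.7%, which matches the stated 80%. A one-sided test would give 89.9%, so two-sided is the right reading.

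**Step 2: the two rules.** Bonferroni rejects when p ≤ 0.05/20 = 0.0025. Holm orders the p-values and rejects the i-th smallest while p(i) ≤ 0.05/(21 − i), stopping at the first failure. Holm's thresholds are 0.05/20 = 0.0025, 0.05/19 = 0.00263, 0.05/18 = 0.00278, …, 0.05/10 = 0.005 at the 11th and 0.05 at the 20th. None is below 0.0025, so every Bonferroni rejection is also a Holm rejection.

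For error control, suppose m₀ hypotheses are true nulls. When Holm first rejects one of them, at least m₀ hypotheses are still in play, so the threshold at that step is at most 0.05/m₀. The chance that any of the m₀ true nulls has a p-value that small is at most m₀ × 0.05/m₀ = 5%, whatever the dependence.

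**Step 3: power at the shared first threshold, planned effect.**

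| Test | Power at 0.05 | Power at 0.0025 |
|---|---|---|
| Paired, n = 8 | 79.7% | 22.9% |
| 8 v 8 | 57.3% | 14.0% |
| 8 v 4 | 39.7% | 6.2% |

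The last column is Bonferroni's power for each comparison. It is also the power at Holm's first step.

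**Step 4: expected true discoveries among 20 tests (simulation).**

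| Setting | Bonferroni | Holm |
|---|---|---|
| Paired, 1.15 SD, 5 real | 1.13 | 1.16 |
| Paired, 1.15 SD, 10 real | 2.26 | 2.43 |
| Paired, 1.15 SD, 20 real | 4.6 | 5.5 |
| The same 20 real, markers correlated at 0.5 | 4.6 | 6.4 |
| 8 v 8, 1.15 SD, 10 real | 1.42 | 1.48 |
| 8 v 4, 1.15 SD, 10 real | 0.62 | 0.64 |
| Paired, 2 SD, 15 real | 11.8 | 13.8 |

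Markers are uncorrelated except in the fourth row. As a check on the Bonferroni column, 20 × 0.229 = 4.6. Repeat runs differ by a few hundredths: for 10 real paired effects, a run of 20,000 replicates gave average power of 23.0% v 24.8%, or 2.30 v 2.48. The gap is almost the same (0.18 against 2.43 − 2.26 = 0.17).

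**Step 5: safety of the switch.** Holm lost no Bonferroni rejection in any simulated data set. Its simulated family-wise error was at most 4.93%. The two methods always agreed on whether there was any discovery at all.

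**The case against.** The strongest case for leaving the text alone is that Bonferroni is valid, prespecified and conservative, and that the family is labelled hypothesis-generating in a pilot. The primary conclusion does not depend on it. All of this stands, and it is why the point is an optional improvement and not an error in the plan.

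It is also fair to object that the gain depends on the scenario shown. At the planned effect with 10 or fewer real effects, Holm adds less than 0.3 of a discovery. The sentences just before the multiplicity rule describe between-arm comparisons, where it adds almost nothing. The gain of two discoveries (11.8 v 13.8) needs 15 of 20 populations to shift by 2 SD. Section 1.4 gives directional expectations for CD8/Treg, for ICOS-positive CD4 cells and for PD-L1, PD-1 and CTLA-4 expression. It gives no figures for large shifts across most cell populations.

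A reader might infer from the 23%, 14% and 6% that choosing Bonferroni causes the low power and that Holm would cure it. The figures do not support that. They follow from the sample sizes and the 0.0025 first step, which Holm shares, and if nothing passes 0.0025 Holm adds nothing.

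The need to fix the family in advance is no argument against Holm, because Bonferroni needs it equally. It is nevertheless a gap. The plan says only that there are about 20 comparisons. It does not say whether the blood, bone-marrow or 300-gene comparisons in Section 8.1.2 belong to the family.

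**Conclusion.** The point holds as a free improvement of small size. That Holm controls the same family-wise error under any dependence and never rejects less is a mathematical property and needs no assumption about these data. Nothing in the documents, such as planned simultaneous intervals, gives a reason to prefer the single-step method.

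The size of the gain does rest on the assumptions listed with the inputs. At the planned effect it runs from 0.03 of a discovery (5 real effects, paired) to about 0.9 (5.5 − 4.6, all 20 real), or 1.8 if all 20 are real and correlated at 0.5 (6.4 − 4.6). Between arms with 10 real effects it is 0.06 (8 v 8) and 0.02 (8 v 4). It becomes material only if many populations shift strongly.

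The documents do not support reading this as a flaw in error control, a cure for low power, or a threat to the primary CD8/Treg test. That test is specified separately and powered at 5%.

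**What to change.** In Section 10.3 and in the synopsis, replace the Bonferroni correction with the Holm step-down procedure at family-wise 5%. Apply it to the same immune-cell family, list the comparisons in that family before analysis, and report Holm-adjusted p-values.

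The cost is one phrase in two places plus the list, which Bonferroni would need as well. SAS, already the planned software, provides the procedure. No data collection changes and no error control is lost. Holm does not supply simultaneous confidence intervals as simply as Bonferroni, but the plan has none to give up.
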